6.3 Handling of Missing Data

All analyses will be based on observed cases (without imputation).

If the intensity of an AE is missing, the event will be considered severe. If relationship of the AE to study drug is missing, the event will be counted as related.

Adverse events will be considered treatment emergent unless it can be determined from the onset or end date information that the event cannot have been treatment emergent.

7. STATISTICAL ANALYSIS

7.1 General Considerations

This is a Phase 3 study to evaluate the safety of daily treatment with RVL-1201 Ophthalmic Solution (oxymetazoline hydrochloride ophthalmic solution, 0.1%) compared to Vehicle (placebo) for the treatment of acquired ptosis over an extended dosing period of 12 weeks.

Subjects will be randomized in a 2:1 ratio of RVL-1201 Ophthalmic Solution to Vehicle into 2 treatment groups and treated for 84 days:

- RVL-1201 Ophthalmic Solution 1 drop in each eye QD in the morning (N = 150)
- Vehicle (placebo) 1 drop in each eye QD in the morning (N = 75)

Descriptive statistics will be used to summarize continuous outcomes (number of subjects [N], mean, standard deviation or standard error of the mean, median, maximum, and minimum) and categorical variables (frequency and percentage) at each assessment time point.

All data collected in the study database will be presented in the listings.

All statistical analyses and reporting will be performed using the SAS® System Version 9.4 or later.

7.1.1 Definition of Baseline

Measures collected prior to dosing on Day 1 will serve as baseline.

7.2 Subject Disposition

Subject disposition, including the number of subjects randomized, treated, and completing the study (and completing each study visit), will be tabulated by treatment group. The percentage of subjects treated and completing the study will be based on the total number randomized.

Discontinuations and the reasons for discontinuation will be summarized. Discontinuations of study medication prior to study completion will also be summarized. Subject disposition will also be summarized by study site.

Eligibility criteria exemptions and protocol deviations will be summarized by treatment group and presented in a listing.

The total number and percentage of subjects included in the safety population will be summarized by treatment group, with percentages based on the total number randomized subjects.

7.3 Demographic and Baseline Characteristics

Subject demographic and baseline characteristics will be summarized using descriptive statistics for the safety population.

Demographic information including age, gender, race, ethnicity and iris color will be summarized. MRD captured at Visit 1 (Screening/Baseline, Day 1) will also be summarized by eye (left eye (OS) and right eye (OD)). Such tables will be supported with individual subject data listings.

Age will be determined as the whole integer number of years from the date of birth (DOB) to the date of the screening visit, i.e., the truncated integer difference between the DOB and Visit 1.

Prior medications will be tabulated. A prior medication is defined as any medication that starts and stops prior to first dose of study medication.

Medical and surgical history classified using the Medical Dictionary for Regulatory Activities (MedDRA) will be summarized descriptively and presented in a listing.

7.4 Concomitant Medications

All concomitant medications listed on the case report form will be provided in data listings in the clinical study report. The frequency distribution based on the generic drug name of all prior and concomitant medications used during the study will be provided for each treatment group.

7.5 Treatment Compliance and Exposure

The amount of opened and unopened medication returned at Visits 2, 3 and 4 will be documented in the CRF to provide an assessment of compliance in the form of percentage compliance for each subject. Compliance is determined by counting opened/unopened bottles. The percent of opened bottles to the total that should have been used during the treatment period will be tabulated.

8. SAFETY MEASURES

Safety data will be presented in tables of descriptive statistics and frequency distribution using the safety population. All summary tables will be supported with individual subject data listings.

8.1 Intraocular Pressure

Descriptive statistics of the observed and change from baseline IOP will be tabulated by visit and treatment group. The descriptive statistics will be presented by eye (left eye (OS) and right eye (OD)).

8.2 Snellen Visual Acuity

The Snellen fraction will be converted to an equivalent logMAR value. The logMAR value is calculated by taking the \log_{10} of the reciprocal of the Snellen fraction. For example, if the Snellen fraction is 20/60, the log MAR value is $\log_{10}(60/20) = 0.477$.

Descriptive statistics of the observed and change from baseline logMAR will be tabulated by visit and treatment group. The descriptive statistics will be presented by eye (left eye (OS) and right eye (OD)). Note that any repeat tests due to refraction issues will be utilized in the analyses.

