Assessment	Screening/Baseline Randomization Day 1	Day 14 (± 3 Days)	Day 42 (± 3 Days)	Day 84 (± 3 Days)	Early Discontinuation
Visit	1	2	3	4	
Study medication accountability	X	X	X	X	X

MRD = marginal reflex distance; OU = both eyes; VA = visual acuity

^a Females of childbearing potential only (females who have started their menstrual cycles).

^b For precise timing of adverse events at each visit, please refer to details of each individual visit in [Section 10](#).

^c Resting blood pressure and heart rate are taken seated after 3 minutes rest.

^d MRD and pupil diameter will be measured from the external photograph.

^e If the corrected or uncorrected VA is 20/80 or better, no additional refraction is necessary. If corrected or uncorrected VA is worse than 20/80 an updated refraction must be performed, which must be used for all VA assessments during the study. The subject must wear the same glasses, if applicable, at each visit. For subjects with surgical monovision correction, VA assessment may be conducted in the near vision eye with a near vision reading card held at approximately 14 inches from the subject's eye.

^f Only tropicamide (Mydriacyl) should be used for this exam. Phenylephrine hydrochloride (Neosynephrine) may NOT be used.

^g Study medication will be dispensed at Day 1 (Visit 1), Day 14 (Visit 2), and Day 42 (Visit 3). Study medication will be administered at the study site on Day 1. Otherwise, study medication will be administered QD in the morning at home daily.

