7. SELECTION AND WITHDRAWAL OF SUBJECTS

7.1. Inclusion Criteria

1. Males or females \geq 9 years of age.
2. Presence of both of the following at Screening/Baseline:
 - a. The MRD, the distance from the central pupillary light reflex to the central margin of the upper lid, must be \leq 2 mm (no visible central pupillary light reflex defaults to 0) in either eye.
 - b. Snellen visual acuity (VA) of 20/80 or better in the same eye as Inclusion Criteria #2a.
3. Females must be 1-year postmenopausal, surgically sterilized, or females of childbearing potential with a negative urine pregnancy test at Visit 1. Females of childbearing potential (females who have started their menstrual cycles) must use an acceptable form of contraception throughout the study. Acceptable methods include the use of at least one of the following: intrauterine (intrauterine device), hormonal (oral, injection, patch, implant, ring), barrier with spermicide (condom, diaphragm), or abstinence.
4. Must be able to self-administer study medication or to have the study medication administered by a caregiver throughout the study period.
5. Must be able to understand and sign an informed consent form (ICF) prior to participation in any study-related procedures. For minor subjects, the subject's parent or legal guardian must provide permission by signing the ICF on behalf of the subject and the subject should provide assent, per Institutional Review Board (IRB) guidelines. If a subject becomes 18 years of age during the study, the subject will need to sign an ICF to continue in the study.

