9.3.2. Snellen Visual Acuity Assessment

Corrected or uncorrected Snellen VA measurement will be performed with the Snellen eye chart using the subject's current corrective lens prescription, if applicable, at a distance equivalent to 20 feet (6 meters). If the corrected or uncorrected visual acuity is 20/80 or better, no additional refraction is necessary. If corrected or uncorrected visual acuity is worse than 20/80, then an updated refraction must be performed. This refraction must be used for all VA and visual field (if applicable) assessments during the study. The subject must wear the same glasses (if applicable) at each visit. The updated refraction can be placed in a trial frame or phoropter for VA assessments, and the trial frame only for visual field (if applicable) assessments.

For subjects with surgical monovision correction, VA assessment may be conducted in the near vision eye with a near vision reading card held at approximately 14 inches from the subject's eye.

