3.3.2 Snellen Visual Acuity Assessment

Corrected or uncorrected Snellen VA measurement will be performed with the Snellen eye chart using the subject's current corrective lens prescription, if applicable, at a distance equivalent to 20 feet (6 meters). If the corrected or uncorrected visual acuity is 20/80 or better, no additional refraction is necessary. If corrected or uncorrected visual acuity is worse than 20/80, then an updated refraction must be performed. This refraction must be used for all VA and visual field (if applicable) assessments during the study. The subject must wear the same glasses (if applicable) at each visit. The updated refraction can be placed in a trial frame or phoropter for VA assessments, and the trial frame only for visual field (if applicable) assessments.

For subjects with surgical monovision correction, VA assessment may be conducted in the near vision eye with a near vision reading card held at approximately 14 inches from the subject's eye.

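### Re-refraction below 20/80 is not limited to Visit 1 and SAP 8.2 uses any repeat, so a post-dose change in acuity may compare two different corrections

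*SAP*

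**What the plan says.** **Trigger.** Protocol 9.3.2 states: "If corrected or uncorrected visual acuity is worse than 20/80, then an updated refraction must be performed". SAP 3.3.2 has the same sentence. Neither names a visit. Footnote e of the schedule (Protocol Table 2 in section 6.1, repeated in SAP section 12) says the same: "If corrected or uncorrected VA is worse than 20/80 an updated refraction must be performed, which must be used for all VA assessments". It is attached to the Snellen row, which is marked at Day 1, Day 14, Day 42, Day 84 and Early Discontinuation.

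**Carry-forward.** SAP 3.3.2 continues: "This refraction must be used for all VA and visual field (if applicable) assessments during the study". Protocol 9.3.2 agrees, and then requires one fixed correction: "The subject must wear the same glasses (if applicable) at each visit".

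**Eligibility.** Protocol 7.1 asks for "Snellen visual acuity (VA) of 20/80 or better in the same eye as Inclusion Criteria #2a". The threshold therefore binds only the eye that meets the lid-position criterion. The fellow eye may be worse than 20/80 at entry.

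**Analysis.** SAP 8.2 converts Snellen fractions to logMAR and plans this summary: "Descriptive statistics of the observed and change from baseline logMAR will be tabulated by visit and treatment group", separately for right and left eyes. It then says that "any repeat tests due to refraction issues will be utilized in the analyses". SAP 7.1.1 takes pre-dose Day 1 measures as baseline. No category of acuity loss is tabulated.

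**The concern.** Corrected Snellen acuity is a listed safety endpoint (Protocol 11.5) in a trial whose only objective is safety. A change from baseline is interpretable when both readings use the same correction. If a poor post-dose reading leads to a new refraction, and the reading under that refraction enters the table, the change mixes any effect on the eye with the effect of better lenses.

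The trigger is one-sided. It acts only on readings worse than 20/80, and a new refraction would be expected to improve such a reading or leave it alone. The eyes affected are those with the worst acuity on treatment. In a purely descriptive table, the maximum is where a single such eye would be seen.

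SAP 8.2 does not say which of two readings at one visit is summarised. It also does not provide for baseline to be re-measured under a later refraction.

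**Working it through.** **Inputs from the documents.** The trigger is acuity worse than 20/80. The conversion is logMAR = log10(Snellen denominator / 20) (SAP 8.2). Planned sizes are 150 and 75 (Protocol 6.2). The documents give no acuity data, so the acuities below are assumptions.

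**Step 1: the plan's own figure.** For 20/60, log10(60/20) = 0.477, as SAP 8.2 states.

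**Step 2: where the trigger sits.** 20/80 is log10(80/20) = 0.602. A fall from 20/20 to 20/80 is 0.602 − 0.000 = +0.602 and triggers nothing. A fall from 20/80 to 20/100 is 0.699 − 0.602 = +0.097 and does. The rule depends on the level reached, not on the size of the loss.

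**Step 3: the loss that could leave the table.** The change is logMAR(first post-dose reading) − logMAR(baseline):

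| Assumed baseline | First reading 20/100 (0.699) | First reading 20/200 (1.000) |
|---|---|---|
| 20/20 (0.000) | +0.699 | +1.000 |
| 20/40 (0.301) | +0.398 | +0.699 |
| 20/80 (0.602) | +0.097 | +0.398 |

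If re-refraction restores the baseline acuity and that repeat is the summarised value, each entry becomes 0. For these readings the range is about +0.10 to +1.00 logMAR per eye.

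**Step 4: effect on the mean.** Take 20/40 to 20/100, with every subject contributing that eye. One eye shifts the mean by 0.398/150 = 0.0027 in the active arm and 0.398/75 = 0.0053 in the vehicle arm. At n = 150, three such eyes shift it by 0.0080 and five by 0.0133.

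**Step 5: the texts side by side.** SAP 3.3 sends the reader to the schedule for the timing of safety assessments, and there the footnote covers every visit. Where the SAP means particular visits, it can say so: MRD at Visit 1 (SAP 3.2.1) and the pregnancy test at named visits (SAP 3.1.4). It does not do so for re-refraction or for repeat acuity tests. A refraction first updated after dosing also sits badly with the footnote's own sentence: "The subject must wear the same glasses, if applicable, at each visit". Under the carry-forward rule, later visits would use the new correction too, so the mismatch with baseline would not be confined to one visit.

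**The case against.** The strongest reply is that the texts can be read together as one refraction fixed at the start. A refraction first done on Day 42 cannot serve assessments already completed. The same-glasses rule points the same way. The 20/80 trigger equals the eligibility threshold, and because the fellow eye need not meet that threshold, the rule has a natural use at Visit 1. Under the literal reading, an eye that cannot be corrected to 20/80 would need a new refraction at every visit. This is a plausible account of what was intended. It remains an inference, because no passage limits the refraction rule or the repeat rule to Visit 1.

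Other parts of the reply stand and limit the point:

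- SAP 8.2 says repeats are used; it does not say they replace the first reading. Nor does it define refraction issues, which could include a repeat after the wrong glasses were worn. Such a repeat would restore comparability with baseline.
- Loss from corneal, retinal or other non-refractive causes would remain in the repeat value. Slit-lamp, staining and fundus examinations look for structural causes separately.
- All data in the database are listed (SAP 7.1). Clinically significant findings can be reported as adverse events (Protocol 9.4.1.1 and 9.6).
- The endpoint is corrected acuity, so a value under an updated correction is not in itself a wrong measurement. The difficulty is the mismatch with baseline.

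A reader might infer that the plan erases treatment-emergent acuity loss, or that it biases the acuity result towards safety. The documents do not support that. It would need the literal reading, an actual post-dose fall below 20/80, a refractive cause, and replacement of the first value. The first and last of these are unsettled in the text, and the other two are unknown.

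**Conclusion.** The point holds as an unresolved analysis rule on a named safety endpoint. Followed literally, the plan allows a post-dose acuity under a new correction to be compared with a baseline under the old one, and only for eyes that read worse than 20/80.

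The effect falls on the maximum and on the visibility of individual losses: about +0.10 to +1.00 logMAR per affected eye for the assumed readings. Arm means barely move. The rule applies alike in both masked arms, so it would affect their comparison only if such falls were more frequent or larger in one arm. The documents do not show that any eye would be affected. The case for acting is that the summarised value can be fixed in advance at little cost.

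**What to change.** **SAP 8.2.** State that a repeat after updated refraction is the analysed value only at pre-dose Day 1, where it becomes the baseline. After dosing, summarise the reading taken with the baseline correction and present any re-refracted value separately.

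**eCRF.** Require both readings to be entered when a visit has two, each identified by the correction used. The documents do not say that both are captured.

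**Reconciliation.** Bring Protocol 9.3.2, SAP 3.3.2 and footnote e of both schedules into line with the same-glasses rule. The reconciled text should say at which visits the refraction rule applies, and which correction is worn for the analysed reading at later visits. If re-refraction after dosing remains possible, a reading with the baseline correction must still be taken at those visits for the SAP rule to work.

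**Cost.** A sentence or two in the SAP, a clarification in the protocol, one extra eCRF field and one extra listing or table, plus a second reading for any eye re-refracted after dosing. The study plans no tests and its size rests on no calculation, so sample size and error rates are unaffected.

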8.3 Pupil Diameter

Descriptive statistics of the observed and change from baseline pupil diameter will be tabulated by visit and treatment group. The descriptive statistics will be presented by eye (left eye (OS) and right eye (OD)).

8.4 Corneal Fluorescein Staining

The status of the cornea epithelium will be graded on a 5-point scale (no staining, trace, middle, moderate, and severe) and will also be assessed for clinical significance (yes or no). The clinical significance results will be tabulated (n, %) by visit and treatment group.

8.5 Slit Lamp Examination

The status of the anterior segment of the eye, including lids, cornea, conjunctiva, anterior chamber, iris, and lens with respect to normalcy, non-clinically significant or clinically significant changes will be tabulated (n, %) by visit and treatment group.

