Safety and Tolerability Assessments: Safety assessment will include bilateral SLE/CFS, measurement of pupil diameter from external photographs, dilated ophthalmoscopy/fundus examination, tonometry, Snellen VA using recent correction, if applicable, vital signs (BP/HR), and collection of adverse events (AEs). Tolerability will be rated by the subject on a 4-point scale.

Criteria for Evaluation:

The safety of RVL-1201 compared to Vehicle will be evaluated by the following endpoints:

1. Comparison of ocular and non-ocular AEs by:
 - a. Frequency
 - b. Intensity
 - c. Relationship to treatment
 - d. Serious adverse events
 - e. Adverse events leading to withdrawal of study medication
2. Comparison of subjects with findings on the following measures:
 - a. Slit-lamp examination
 - b. Corneal fluorescein staining
 - c. Pupil diameter
 - d. Dilated ophthalmoscopy/fundus examination
 - e. Tonometry
 - f. Snellen VA (corrected)
 - g. Vital signs (BP/HR)
3. Comparison of tolerability as measured by the tolerability scale

Statistical Methods:

A detailed Statistical Analysis Plan (SAP) will be finalized prior to database lock. Descriptive statistics (n, mean, median, standard deviation [SD], minimum, and maximum for continuous data; frequencies and percentages for categorical data) will be used to summarize study data. No statistical tests will be performed for any of the assessments.

Sample Size:

The sample size for this study is not based on statistical calculations. The sample size was based on the need to obtain sufficient safety data to meet regulatory obligations for the development of RVL-1201.

Analysis Populations:

The Safety population will be used for all analyses. The Safety population includes all subjects who receive at least one dose of double-masked study treatment and have at least one post-dose visit. Subjects will be analyzed according to the treatment received.

Safety Analyses:

Safety endpoints will be reported on the Safety population. Safety assessments include AEs, vital signs (BP/HR), ophthalmic assessments (Snellen VA, bilateral SLE/CFS, measurements of pupil diameter from external photographs, dilated ophthalmoscopy/fundus examination, and tonometry), and a tolerability assessment. Safety assessment will be based on descriptive statistics utilizing actual and change from baseline values, where appropriate, and individual subject listings.

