11.5. Safety Endpoints

The safety of RVL-1201 compared to Vehicle will be evaluated by the following endpoints:

1. Comparison of ocular and non-ocular AEs by:
 - a. Frequency
 - b. Intensity
 - c. Relationship to treatment
 - d. Serious adverse events
 - e. Adverse events leading to withdrawal of study medication
2. Comparison of subjects with findings on the following measures:
 - a. Slit-lamp examination
 - b. Corneal fluorescein staining
 - c. Pupil diameter
 - d. Dilated ophthalmoscopy/fundus examination
 - e. Tonometry
 - f. Snellen VA (corrected)
 - g. Vital signs (BP/HR)
3. Comparison of tolerability as measured by the tolerability scale.

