2.5 Study Plan/Procedures

This will be a Phase 3, randomized, multicenter, double-masked, placebo-controlled study to evaluate the extended safety of RVL-1201 Ophthalmic Solution compared to Vehicle (placebo) for the treatment of acquired ptosis. The study will be conducted over 84 days (12 weeks).

Eligible subjects will be randomized in a 2:1 ratio to one of 2 treatment arms and treated for 84 days:

- RVL-1201 Ophthalmic Solution 1 drop in each eye QD in the morning (N = 150)
- Vehicle (placebo) 1 drop in each eye QD in the morning (N = 75)

Both eyes will be treated and assessed.

Following screening evaluations at the Screening/Baseline visit (Day 1), a determination of eligibility will be made, and eligible subjects will be randomized and receive study medication.

Study medication, RVL-1201 or Vehicle (placebo), will be provided in identical-appearing unit-dose vials. The identity of the study medications will be masked to the subject, Investigator, study personnel responsible for ophthalmic evaluations, and Sponsor personnel.

Subjects (or their caregiver, if necessary) will administer study medication QD in the morning during the study period.

Safety follow-up visits will be conducted at Day 14 (Visit 2), Day 42 (Visit 3), and Day 84 (Visit 4).

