8.6 Ophthalmoscopy and Fundus Exam

The status of the fundus with respect to normalcy, non-clinically significant or clinically significant changes will be tabulated (n, %) by visit and treatment group. The summaries will be presented by eye (left eye (OS) and right eye (OD)).

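### SAP 8.5 tabulates slit-lamp status by visit with no within-subject reference to Day 1 and no stated unit, so new findings cannot be separated from old or resolved ones and the subjects-with-findings endpoint is undefined

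*SAP*

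**What the plan says.** SAP 8.5 places the anterior segment, with six parts named from lids to lens, into three categories: normal, not clinically significant, clinically significant. These are to be reported "with respect to normalcy, non-clinically significant or clinically significant changes will be tabulated (n, %) by visit" and treatment group. That is the whole specification. It names no shift from baseline, no new-or-worsened category, no unit and no denominator.

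The neighbouring text says more:

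- SAP 8.6, on the fundus, uses the same three categories but adds: "The summaries will be presented by eye", left and right.
- SAP 8.1 to 8.3 specify observed values and change from baseline, by eye. SAP 8.8 specifies change from baseline for vital signs.
- SAP 7.1.1 defines the reference point: "Measures collected prior to dosing on Day 1 will serve as baseline". The Schedule of Procedures has a slit-lamp exam at Day 1 and at every later visit.
- SAP 2.5 states: "Both eyes will be treated and assessed".
- Protocol 11.5 sets the endpoint at subject level: "Comparison of subjects with findings on the following measures", with the slit-lamp exam first on the list.
- The Protocol synopsis, under Safety Analyses, says: "Safety assessment will be based on descriptive statistics utilizing actual and change from baseline values, where appropriate, and individual subject listings".

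Neither document defines a finding, or says how two eyes become one subject.

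**The concern.** This is a safety-only trial, and the slit lamp is one of its main means of seeing what a daily drop does to the front of the eye. The question is whether eyes acquire or worsen findings on treatment, and in how many subjects per arm. Percentages by visit are margins. They say how many are abnormal on Day 1 and how many on Day 84, but not whether these are the same people. They are also based on observed cases (SAP 6.3), so the subjects behind the percentages can differ from visit to visit.

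The missing unit is a second gap. With two eyes examined per subject, a count of eyes and a count of subjects can differ by up to a factor of two, and the protocol's endpoint is about subjects. If the unit and the definition of a finding are settled after the data are seen, the reported rate depends on that choice.

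**Working it through.** The plan gives no slit-lamp rate, performs no tests and derives no sample size, so there is no figure of its own to reproduce. The check has three parts.

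**1. What each section specifies**

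| SAP section | Reference to baseline | Unit |
|---|---|---|
| 8.1–8.3 IOP, visual acuity, pupil | observed and change | by eye |
| 8.4 corneal staining | none stated; clinical significance only | not stated |
| 8.5 slit lamp | none stated | not stated |
| 8.6 fundus | none stated | by eye |
| 8.8 vital signs | observed and change | subject |

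The word *changes* in 8.5 could be read as change from baseline. But it stands in a list of status categories alongside normalcy, and no rule says how a change would be derived.

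**2. What a by-visit table can show**

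Inputs from the documents: N = 150 (RVL-1201) and 75 (Vehicle). Assumptions, since the documents give no rates: baseline prevalence b, onset i among those normal at baseline (10% RVL-1201, 4% Vehicle), and resolution r among those abnormal at baseline.

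- Prevalence at a later visit: p = b(1 − r) + (1 − b)i
- Pre-existing share of abnormal subjects when r = 0: b/p
- Resolution that exactly cancels onset: r* = (1 − b)i/b

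| b | p RVL-1201 (r = 0) | p Vehicle (r = 0) | Difference (points) | Pre-existing share, RVL-1201 | r*, RVL-1201 |
|---|---|---|---|---|---|
| 5% | 14.5% | 8.8% | 5.7 | 34% | none (above 100%) |
| 10% | 19.0% | 13.6% | 5.4 | 53% | 90% |
| 30% | 37.0% | 32.8% | 4.2 | 81% | 23.3% |
| 50% | 55.0% | 52.0% | 3.0 | 91% | 10.0% |
| 70% | 73.0% | 71.2% | 1.8 | 96% | 4.3% |

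Three cases at b = 30%. New findings are the same in all three: 150 × 0.7 × 0.10 = 10.5 subjects (7.0%) on RVL-1201 and 75 × 0.7 × 0.04 = 2.1 (2.8%) on Vehicle.

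- *Nothing resolves.* RVL-1201 goes from 30.0% to 37.0% and Vehicle from 30.0% to 32.8%. The rises of 7.0 and 2.8 points equal the new-finding rates, so the table with its Visit 1 column recovers them.
- *23.3% resolves in both arms.* RVL-1201: 0.30 × 0.767 + 0.07 = 30.0%. Vehicle: 0.23 + 0.028 = 25.8%. The 4.2-point difference survives, but it reads as improvement on Vehicle and no change on drug.
- *Resolution differs: 23.3% on RVL-1201, and r* = 0.7 × 0.04/0.3 = 9.3% on Vehicle.* Both arms stay at 30.0% and the table shows nothing. The protocol's introduction credits oxymetazoline at lower concentrations with reducing hyperemia, so a drug effect on resolution cannot be ruled out. No rate is given.

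**3. What the unit does**

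Take 15 affected subjects of 150, which is 10.0% by subject. Counted over 300 eyes, the rate is 15/300 = 5.0% if none is bilateral, 22.5/300 = 7.5% if half are, and 30/300 = 10.0% if all are. Separate left and right tables do not settle the subject rate either: with 15 of 150 abnormal in each eye, the affected subjects number anywhere from 15 (10%, all bilateral) to 30 (20%, none bilateral).

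**The case against.** The best defence is that the by-visit table includes Visit 1. A reader can compare each arm with its own starting level and with Vehicle, and the first case above shows that this is enough when nothing resolves and the same subjects attend. That stands. It also defeats a tempting precision argument, that the status difference between arms is several times noisier than a difference in new findings. That comparison ignores the Visit 1 column: when nothing resolves, each subject's change is itself the new-finding indicator, and the precision is the same. What the defence does not cover is resolution and changing attendance, where margins alone cannot give the number of new findings.

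Second, adverse events offer another route. Under Protocol 9.4.1.1, pre-existing conditions that worsen can become adverse events, and so can test abnormalities that are symptomatic, clinically significant or treated. SAP 8.9 then counts subjects and has a rule for bilateral events. This narrows the gap but does not close it. A new finding judged not clinically significant, without symptoms or treatment, need not be an adverse event, and Protocol 9.6 leaves changes belonging to the disease under study to the investigator's judgement. For such findings only the 8.5 status table and the listings remain, and listings do not compare arms. The staining table in 8.4 reports clinical significance, not grade, so it is no substitute for mild corneal change.

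Third, the protocol asks for change from baseline only where appropriate, and table shells are still to be prepared (SAP 10). Both points are true. A shift table is therefore an improvement rather than a breach of the protocol, but the unit and the definition of a finding belong in the SAP and should not be left to a shell.

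**Conclusion.** The point holds as a gap in specification with a better method at hand. SAP 8.5 gives net prevalence by visit, without a within-subject link to Day 1 and without a unit, and the endpoint in Protocol 11.5 is left undefined. What is lost is mainly an arm-level summary of new findings that are not clinically significant. Its size is unknown: on the assumed onset rates it runs from little, at low baseline prevalence or with no resolution, to complete cancellation at b = 30% with differing resolution.

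Four stronger readings go beyond the documents:

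- *Pre-existing abnormalities swamp new ones.* This depends on a prevalence that is not given. At b = 5% and 10% onset, pre-existing findings are only 34% of the total.
- *The endpoint will not be produced.* If n counts subjects, the table does give subjects with a finding at each visit. The endpoint is undefined, not absent.
- *Lens and lid abnormalities at baseline will hide corneal ones.* No baseline lens rate is documented, and if status is tabulated by structure, as the list in 8.5 suggests, one structure cannot mask another.
- *Two eyes will be pooled as independent.* No section says so, and 8.1 to 8.3 and 8.6 all present by eye.

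**What to change.** In SAP 8.5, present the by-visit status table by eye and by structure, matching the by-eye layout of 8.6. Add to both 8.5 and 8.6:

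- (a) a shift table by structure and arm, from Day 1 status to worst post-baseline status;
- (b) n (%) of subjects per arm with a new or worsened finding in at least one eye, where new or worsened means a higher category than on Day 1 in the same eye and structure, over subjects with a Day 1 exam and at least one later exam.

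Item (b) would serve as the stated definition of the Protocol 11.5 endpoint for these exams. For the fundus, which is scheduled only on Day 1 and at Day 84 or early discontinuation, the worst post-baseline status will usually be the single later exam. One limit should be noted in the text: a different finding within the same category and structure does not register as a shift and remains visible only in the listings.

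The cost is about one extra table per exam, from data already collected. Visits, procedures and sample size are unaffected.
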